Since the beginning of the pandemic, Washington University in St. Louis (WUSTL) has worked closely with the St. Louis community, including many school districts and organizations that support underserved populations.⁹ The PI, [name], has met regularly with school superintendents throughout the region, including those in underserved school districts, since July 2020 to provide consultation on best practices for conducting in-person schooling. Additionally, he is co-PI on a current RADx-UP grant evaluating messaging strategies regarding performing weekly testing in schools dedicated to children with intellectual and developmental disability. Since November 23, 2020, we have performed approximately 4500 SARS-CoV-2 PCR tests in these staff and students. Furthermore, our team has collaborated with CDC to rigorously assess school-based COVID-19 transmission; we have performed another 500 tests in symptomatic students and asymptomatic contacts in that study (pilot data to be published in *MMWR* March 22, 2021). Finally, the faculty and staff of WUSTL Brown School of Social Work and Public Health have forged strong partnerships with community organizations to learn about barriers to SARS-CoV-2 testing, attending in-person school, and vaccination. These community partners have been essential in providing services, messaging, and support to our underserved communities. In summary, the research team and community partners have the experience and are well-positioned to implement the proposed work quickly and complete it successfully.

In this proposal, we will test the hypothesis that frequent screening testing will provide additional benefit, beyond current school-based mitigation strategies, to prevent SARS-CoV-2 transmission. We will complete a cluster randomized trial to compare the incidence of school-based SARS-CoV-2 transmission between weekly surveillance testing of students and school

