| Consent students and staff to receive surveillance testing | • | | | | | | | |
| Conduct surveillance testing in select schools | • | • | • | • | | | | |
| Assess school-based transmission with use of testing | • | • | • | • | • | | | |
| Collect weekly number of school cases, contacts, and in-person enrollment | • | • | • | • | | | | |
| Analyze testing data | | | | | • | • | | |
| Conduct listening sessions & Interviews | • | | | • | | | • | |
| Conduct qualitative analysis | | • | | | • | | | • |
| Share data with Duke coordinating center | • | • | • | • | • | • | • | • |
| Disseminate results | | | • | | • | | | • |

In this proposal, quantifiable milestones will be established in regards to testing. We propose that in the first 3 months post award (Q1), we will perform approximately 3,000 tests. In Q2 and Q3, we estimate approximately 5,000 and 8,000 tests will be performed. In Q4, forecasting a potential winter surge of COVID-19, we estimate a total of 10,000 tests. We estimate that approximately 50%-60% of the testing will occur in adult school staff members based on our current RADx-UP experience. Since we are primarily testing in middle and high schools, approximately 30%-40% of the tests will be done in students between the ages of 11 and 18 years of age.

We have established a process with our testing lab, informatics professionals, and study team to reliably obtain tests; however, trust in the test and the importance of testing will be important to maximize participation. We will work closely with our CAB, community partners, and messaging experts to mitigate this risk and maximize participation. Finally, we have identified additional schools to participate if one or more of the selected schools remain virtual, but could also include these additional schools if testing volume in the core schools proves to be lower than expected.

Study Setting and Populations.

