Symptomatic and/or Exposure Testing: All schools participating in the study will have access to ShieldT3 saliva SARS-CoV-2 PCR testing for students, staff, family members, and/or household members who exhibit symptoms of COVID-19 or have a known exposure. This testing will be provided for both virtual and in-person staff and students. Test samples will be collected in a designated area in each school building for those individuals attending or working in the in-person environment.. For those in virtual learning, or those who are family members and/or household members a drive-up testing area will be available at each site. In situations where transportation is limited, home visits will be offered.

Contact/Data Elements Survey:

Case/Contact Interviews

If any of these individuals or other students/staff present in the school setting are positive for COVID-19, contact tracing will be performed by their school districts per local/state guidance. As part of their contact tracing, individuals will be informed that they may be contacted by a member of the study team to see if they would like to provide additional information via participating in our research. Our research team will contact any cases and their known contacts in the school setting, as provided by the schools. After consent and assent (for those 8-17) is obtained, we will ask them the types of questions listed below. A separate case interview will also be conducted for any known contacts that have a subsequent positive COVID test.

Data Elements Survey

Those who have signed a consent for screening testing will be asked these data elements. Additionally, anyone who has symptomatic testing performed for the purpose of this study and/or was identified during contact tracing, will be asked to provide additional information via participating in our research. Once consent [consent information sheet 14Apr2021] is obtained via phone, Zoom, email or in person, we will ask them questions. Individuals who have agreed to referral and indicate certain needs or resource limitations will be referred to community partners. This will be done through information being provided to the community partner for follow up with the individual.

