Follow-up Protocols: Testing results will be available within 24 to 72 hours. All students, staff, and household members with positive results will be notified by [name] and/or a member of the study team and information regarding appropriate isolation and quarantining for contacts will be provided to comply with prevailing National/County health department recommendations. Additional financial and social services needed for the student and family due to isolation and/or quarantine procedures may be coordinated with the school and community partners. Finally, all positive individuals may have a 3-week phone call follow-up to inquire about the outcome of their illness including the need to seek medical attention and/or be hospitalized. For those in the contact arm, there might be additional questions if the

individual tests positive related to: activities, behaviors, and potential school based exposures.

Assessment of School Mitigation Strategies: Ascertaining the mitigation practices in place for each school is essential for evaluating the impact of additional testing on school transmission. A school-based mitigation strategy survey (Appendix 1), developed in conjunction with the CDC and utilized in prior school-based investigations, may be completed by each school at the beginning of the project. Questions in this survey will include: method of instruction (e.g., hybrid, type of hybrid, fully in-person) and date implemented, masking recommendations and perceived compliance, distancing in classrooms, use of physical barriers (e.g., Plexiglas), location and processes for eating lunch, and mitigation strategies used in extracurricular activities (e.g., sports, choir, band). Schools will also be asked about their quarantine rates and new school based cases/contacts on a weekly basis. This will help understand the rates of transmission in the schools.

Assessment of School-based Transmission: The primary outcome for this study will be the average of the secondary attack rate of school-based transmission per case at each school. For example, if a case has 10 contacts and 2 become infected, the secondary attack rate for that case would be 20%.

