School-based transmission will be determined by two methods. First, all close contacts of an infectious case in the school, identified through contact tracing by school staff and administrators, will be approached to participate in the study (as described above). Those electing to participate will undergo a contact interview (Appendix 2) to understand their behaviors and potential other COVID-19 exposures. Furthermore, the school contact tracer will complete a survey on the relationship of the case to each contact that provides information on the location of the exposure (e.g., classroom, lunch, extracurricular activity), distance between case and contact, use of barriers, masking adherence, and total amount of time the contact was exposed to the case (Appendix 3). The contacts will be offered testing 5-7 days after a school exposure. All contacts testing positive will undergo an independent review by five study team members using the information obtained from the case interview, contact interview, and contact tracing interview to determine whether a school-based transmission has occurred. These transmission events will be classified into the following categories with standardized definitions that were developed in conjunction with the CDC: probable, possible, unlikely, and unable to determine.

The second method to evaluate school-based transmission will be to collect weekly data from the schools, as participation in the above individual assessments is unlikely to reach 100%. The additional data to be collected will include total number of new staff and student cases, total number of new contacts, and number of school-based contacts that become new cases during their quarantine period. The secondary transmission rate will be calculated based on the number of positive school-based contacts per positive case. This method will provide the most conservative/greatest estimate of school-based transmission without knowledge of an individual's exposure to a potential household or community case.

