Power calculation: A cluster randomized trial (CRT) will be conducted at 12 schools that provide symptomatic SARS-CoV-2 testing to students and staff. Schools will be randomized 1:1 to either screening testing plus symptomatic testing, or symptomatic testing only. All participants including students and staff will receive the same assignment within a given school. The primary outcome is transmission rate, defined as the ratio of the number of contacts testing positive for SARS-CoV-2 to total number of contacts for each school-based case. We hypothesize that schools performing screening testing will have lower transmission rates than routine symptomatic testing. We expect that transmission rates with screening testing or routine symptomatic testing will be 2% and 8%, respectively. With the assumptions that the intracluster correlation coefficient (ICC) is 0.02 and the standard deviation of transmission rate is 0.22, 6 schools in each arm with an average of 117 participants per school will achieve 80% power to detect a difference in transmission rates between the two study arms using a two-sided t-test at a significance level of 0.05 (Table 3). PASS 15.0 was used to conduct this power analysis.

Table 3. Sample Size

| ICC | Standard deviation | # of participant per school |
|------|--------------------|-----------------------------|
| 0.01 | 0.25 | 83 |
| | 0.30 | 188 |
| | 0.33 | 376 |
| | 0.35 | 803 |
| 0.02 | 0.22 | 117 |
| | 0.23 | 164 |
| | 0.24 | 252 |
| | 0.25 | 486 |
| 0.03 | 0.20 | 221 |
| | 0.21 | 806 |

Analysis plan: The generalized estimating equation (GEE) model with appropriate link function (e.g., identity for primary outcome) will be used to analyze the CRT data, in which the correlation among participants within each school needs to be considered. The autoregressive of first order as a working correlation structure will be used, and participants with missing values will be excluded from the GEE analysis. The GEE model includes the group indicator and other potential factors, including: race/ethnicity, insurance status, age, gender, underlying diagnoses, masking, distancing, ventilation, location of transmission. Least square means for the primary outcome per group will be estimated, and the standard errors will be calculated with the GEE sandwich method when accounting for within-school correlation. All analyses will be conducted using SAS (SAS Institute, Cary, NC) at the two-sided significance level of 0.05.

Data Management.

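### The stated comparison is incidence of school-based transmission, but both planned measures condition on detected cases, and Section E has no estimate per enrolled person

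*Combined protocol and SAP*

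**What the plan says.** - **Objective (Section A).** The trial will "compare the incidence of school-based SARS-CoV-2 transmission between weekly surveillance testing of students and school" staff and testing of symptomatic people only. The hypothesis is that frequent screening helps prevent transmission beyond existing mitigation.
- **Primary outcome (Section D1, Assessment of School-based Transmission).** The definition reads: "The primary outcome for this study will be the average of the secondary attack rate of school-based transmission per case at each school". The worked example there is a case with 10 contacts, 2 infected, giving 20%.
- **Primary outcome (Section E, Power calculation).** The transmission rate is "defined as the ratio of the number of contacts testing positive for SARS-CoV-2 to total number of contacts for each school-based case", with 2% expected under screening and 8% under symptomatic testing.
- **Second measure (Section D1).** "The secondary transmission rate will be calculated based on the number of positive school-based contacts per positive case".
- **How cases are found (Section D1).** All schools offer tests to people "who exhibit symptoms of COVID-19 or have a known exposure". Schools randomized to screening add weekly tests. Contacts are traced from cases once these are known.
- **Model (Section E, Analysis plan).** A GEE with group indicator and further factors: "race/ethnicity, insurance status, age, gender, underlying diagnoses, masking, distancing, ventilation, location of transmission". Index-case symptoms and route of detection are not named, although the list is introduced as open. No outcome per enrolled person or per unit of time is defined.
- **Data available.** The timeline table in Section C has the line "Collect weekly number of school cases, contacts, and in-person enrollment". Section D1 adds the weekly "number of school-based contacts that become new cases during their quarantine period". Section F has potential transmission events monitored, without a by-arm estimate.

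**The concern.** Recorded school transmissions per enrolled person are the product of three factors: detected cases per enrolled person, contacts per case, and the share of contacts who become positive. The primary is the third factor alone. The second measure is the product of the last two. Neither contains cases per enrolled person, which weekly testing should move most directly: up by finding infections without symptoms, and down by preventing later ones.

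The cases that supply the denominator are also selected differently by arm, after randomization. Screening schools contribute index cases found by routine weekly tests, and control schools do not. If those added cases infect a smaller share of their contacts, the average falls in the screening arm even though nothing was prevented.

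At stake is the reading of the result. A null primary could be taken as no prevention, and a positive one as incidence averted, when the primary on its own supports neither statement.

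**Working it through.** **1. The plan's own figure.** Inputs from Section E: difference 6 points, SD 0.22, ICC 0.02, 117 per school, 6 schools per arm.

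- Design effect = 1 + 116 x 0.02 = 3.32.
- Effective n per arm = 6 x 117 / 3.32 = 211.4.
- SE = sqrt(2 x 0.22² / 211.4) = 2.14 points; 6 / 2.14 = 2.80.
- Power by normal approximation = 0.80, as stated.

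The sample size is therefore not in question here. No sample size for incidence can be derived, because the documents give neither baseline incidence nor school enrolment.

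**2. Identity.** Recorded transmissions = cases x contacts per case x share positive. This is exact for the mean of per-case shares when contacts per case are equal, as below.

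**3. Prevention that the primary cannot show.** From the plan: 8%, and 10 contacts per case (the worked example). Assumed: 20 detected cases per control school; 10 cases with 5 contacts each in a screening school of equal enrolment.

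| | Cases | Contacts per case | Primary | Positives per case | Transmissions |
|---|---|---|---|---|---|
| Control | 20 | 10 | 8% | 0.8 | 16 |
| Screening | 10 | 5 | 8% | 0.4 | 4 |

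Transmissions fall by 75% (ratio 4/16 = 0.25). The primary shows no difference. The second measure shows half, because it registers the fall in contacts but not the fall in cases.

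**4. A shift towards benefit with no prevention.** Assumed: every school in both arms has 20 symptomatic cases at 8%, plus A other cases at share a, with 10 contacts each. Screening finds a fraction f of the others and control finds a fraction g. True transmissions are equal in the two arms.

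Measured primary in an arm finding a fraction x = (20 x 8% + xA x a) / (20 + xA).

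| A | a | f | Screening primary | Shift, g = 0 | Shift, g = 10% | Shift, g = 25% |
|---|---|---|---|---|---|---|
| 20 | 2% | 50% | 6.00% | 2.0 | 1.45 | 0.8 |
| 40 | 2% | 50% | 5.00% | 3.0 | 2.0 | 1.0 |
| 20 | 8% | 50% | 8.00% | 0 | 0 | 0 |

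Shifts are in percentage points, against a planned effect of 6. Over A = 10 to 40, a = 2% to 8% and f = 25% to 50%, the range is 0 to 3.0 points at g = 0. It is smaller when control finds some of the others, which exposure testing makes likely.

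**5. What the shift does to the test depends on the unit.** With 117 units per school (SE 2.14 points), a 2- or 3-point shift raises two-sided rejection on 10 df from 5% to about 14% or 25%. The primary averages over cases, however. With 20 to 40 cases per school and the same SD and ICC, the SE is 3.3 to 2.7 points and rejection is about 8% to 10% or 13% to 17%. The plan does not settle the unit, so none of these rates is firm.

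**6. The enrolment-based rate has its own detection effect.** In the setting of step 4 with g = 0, recorded transmissions in a screening school are 16 + fA x 10 x a. This runs from 16.5 (A = 10, f = 25%, a = 2%) to 32 (A = 40, f = 50%, a = 8%), a ratio to control of 1.03 to 2.0 with no true effect. Restricting to symptomatic index cases gives 16 vs 16 and 8% vs 8%.

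**7. Precision of the rate ratio.** Take 16 vs 4 transmissions per school and an assumed between-school SD s of the log rate. SE(log ratio) = sqrt((2s² + 1/16 + 1/4) / n), with n schools per arm and t on 2n − 2 df.

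| s | n per arm | 95% CI for ratio 0.25 |
|---|---|---|
| 0.5 | 6 | 0.11 to 0.57 |
| 0.5 | 8 | 0.13 to 0.50 |
| 1.0 | 6 | 0.06 to 1.00 |
| 1.0 | 8 | 0.08 to 0.79 |

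Six per arm follows Section E; eight follows the sixteen schools in Sections C and D1.

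**The case against.** The word incidence appears in one introductory sentence. A secondary attack rate is itself an incidence proportion among exposed contacts, and Section E frames its hypothesis in terms of transmission rates. The attack rate also depends less on how much infection enters from the community, which Section C calls an important dependency. A rate per enrolled person depends on it directly, with only 6 to 8 schools per arm. These points stand as reasons to keep the primary. They do not supply the missing estimate, because risk per traced contact cannot register fewer cases or fewer contacts.

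Control schools are not limited to symptomatic people: exposed persons can be tested, and contacts are offered a test 5 to 7 days after exposure. That stands and makes zero detection of other cases the extreme assumption. The covariate list is open and symptoms are asked in interviews, so adjustment is possible, but it is not prespecified.

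A reader might infer more in two ways. The first is that the primary will produce a false benefit of known size, or a false-positive rate of 14% to 25%. The documents give no infectivity or detection fractions, zero shift is within the range, and those rates rest on 117 units per school. The second is that equal recorded transmissions prove there was no benefit. Suppose a screening school records 80 cases at 2% with 10 contacts each, hence 16, the same as control. If the 60 extra cases also existed unseen in control at 2%, control truly had 16 + 60 x 10 x 2% = 28, and screening did reduce transmission. Recorded counts alone do not settle it.

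**Conclusion.** The gap is real. The plan names incidence as its comparison, both its measures condition on detected cases, detection differs by arm by design, and Section E estimates nothing per enrolled person. That the primary cannot register changes in cases or in contacts per case follows from its definition and needs no assumption; the 75% example rests on assumed counts. The shift towards benefit is a possibility, not a finding: 0 to 3 points under the assumed inputs when control finds no other cases, and 0.8 to 2.0 points in the two non-zero scenarios tabulated when it finds 10% to 25%.

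This does not make the primary invalid or call for replacing it. It is interpretable as risk per traced contact, and it should not be read alone as incidence prevented. Nor does the enrolment-based rate become the unbiased answer, since added detection raises it in the screening arm. The addition is worth making because it is cheap and uses counts already scheduled for collection.

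**What to change.** Keep the primary. In Section E, add:

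1. **A secondary by-arm comparison** of positive school-based contacts per 100 in-person enrolled per school-week, from the weekly school counts. Use one total per school over common calendar weeks, a log link with an enrolment offset, and a t reference on schools minus 2 df. Report the rate ratio with its 95% CI.
2. **The components beside it:** cases per 100 enrolled and contacts per case, by arm, so that readers see which factor moved.
3. **A sensitivity analysis** of both the primary and the rate, limited to index cases who had symptoms at any time, whichever test found them. State that this reduces the detection difference but may not remove it, since weekly testing can also find mildly symptomatic people who would not have sought a test.
4. **One sentence of interpretation:** the primary measures risk per traced contact and is not read alone as incidence prevented. Do not require all results to agree before prevention is claimed. Such a rule would block the 75% reduction in the example, where the primary has no direction.

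**Cost.** A paragraph and a table. Cases, contacts, positive contacts and in-person enrolment are already named as data to be collected. Index-case symptoms are asked only in interviews of consenting cases, so item 3 uses that subset or needs one yes/no column on the weekly form.

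**Downside.** Intervals may be wide (0.06 to 1.00 in the least favourable case shown), and greater detection raises recorded transmissions in the screening arm. The report should say both.

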If a student is 18 to 21 years of age and is not cognitively able to provide consent/assent, consent will be obtained from the legally authorized representative. Children 8-17 years of age who are developmentally able will provide assent. Children age 5-7 will not be providing

assent due to their age and development. The consenting/assenting process will be done virtually, in person or by phone.

Contact/Data Elements Survey Consent

Interviews might be eligible for a contact interview if they are a known contact in the school. Additionally, all parents are eligible for the data elements survey regardless of type of testing (screening vs symptomatic/exposure). Prior to completing contact interviews, verbal consent and assent will be obtained from students, staff, and household members as appropriate. Prior to completing the data elements survey, consent will be obtained from the individual completing the survey. Assent will not be obtained for the data elements survey due to lack of student participation in the survey and nature of the questions. As appropriate, a copy of the consent and assent information will be emailed.

Strategy for Sample Collection and Processing.

At the testing site(s), 500 uls of saliva will be collected from each subject under the supervision of a trained research team member. For those in surveillance testing, participants will also have the option of providing the sample at home and bringing it to the school. These individuals might also provide their sample to a family member to bring to the school for drop off. We will provide what is needed to obtain the sample at home. If a participant becomes symptomatic while at school, a study team member may be able to obtain additional samples from those individuals in addition to their weekly testing. If a study team member is not available at the school, these individuals will be referred to outside testing facility.

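### The five-member review that decides whether a positive contact was infected at school is not masked to school or arm, and the plan does not say whether its result enters the primary outcome

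*Combined protocol and SAP*

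**What the plan says.** Section D1, *Assessment of School-based Transmission*, gives the primary outcome as "the average of the secondary attack rate of school-based transmission per case at each school". It then names two methods of determining school-based transmission.

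- **First method.** "All contacts testing positive will undergo an independent review by five study team members". They work from three sources (interviews with the case and the contact, and the contact tracer's account), and their task is "to determine whether a school-based transmission has occurred". The result is one of four grades: "probable, possible, unlikely, and unable to determine". The grades follow "standardized definitions that were developed in conjunction with the CDC".
- **Second method.** Schools report weekly counts, and the rate is the number of positive school contacts per positive case. No review is involved.

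Section E, *Power calculation*, defines the primary outcome differently, as contacts testing positive divided by all contacts for each school-based case. The review is not part of that definition.

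The documents do not describe masking of the reviewers, redaction of the files, a rule for disagreement, or which of the four grades count as transmission. The word independent is not defined. It may mean that the five judge separately from one another; it does not say that they are masked.

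**The concern.** The trial is open by design, because a whole school either runs weekly screening or does not. The team's hypothesis has a direction: screening lowers transmission. The grade requires someone to weigh a school exposure against household and community exposures, and the line between possible and unlikely leaves room for judgement. If reviewers can tell the arm, they may lean toward unlikely in screening schools or toward possible in symptomatic-only schools, without intending to. Either lean creates a difference between arms that is not an effect of screening. None of the covariates listed for the GEE model in Section E would correct it.

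**Working it through.** **Step 1. Does the review reach the primary outcome?**

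| Place | Numerator | Uses the review? |
|---|---|---|
| D1, primary outcome read with the first method | contacts judged infected at school | yes, on a natural reading |
| D1, second method | positive school contacts, from weekly counts | no |
| E, *Power calculation* | contacts testing positive | no |

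D1 and E are both current text, and neither is said to govern.

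**Step 2. Could reviewers infer the arm?** This is an inference from four places.

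- Everyone in a school has the same assignment (Section E), so knowing the school gives the arm to anyone who knows the allocation.
- At the testing sites saliva is "collected from each subject under the supervision of a trained research team member" (D1, *Strategy for Sample Collection and Processing*). Study team members also label and transport the weekly screening specimens, which exist only in screening schools (D1, *Screening Testing*).
- The principal investigator and a co-investigator take part in a quarterly data review under a plan to watch for differences between the two strategies (Section F).
- The survey topics in D1 include earlier testing, type of test and symptoms, and case timing is anchored on symptom onset or, if asymptomatic, on the sample. An asymptomatic case points toward a screening school, but imperfectly, because exposure testing is offered in both arms.

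**Step 3. Reproduce the plan's own figure.** Inputs from Section E: 6 schools per arm, 117 participants per school, ICC 0.02, SD 0.22, difference 0.08 − 0.02 = 0.06, two-sided alpha 0.05.

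- Design effect = 1 + (117 − 1) × 0.02 = 3.32
- Per arm, 6 × 117 = 702; effective number = 702 / 3.32 = 211.4
- SE = sqrt(2 × 0.22² × 3.32 / 702) = 0.0214
- Power = Φ(0.06 / 0.0214 − 1.96) = 0.801

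This agrees with the stated 80% (normal approximation), so 2.14 points is the plan's implied standard error.

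**Step 4. Illustrative size.** Assumptions: no true difference; 5% of contacts positive in both arms; the 702 per arm treated as contacts; the adjudicated rate is primary and has the SE from Step 3.

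- Positives per arm: 0.05 × 702 = 35
- Reclassifying 20% of one arm's positives: bias b = 0.20 × 0.05 = 0.01
- Reclassifying 40%: b = 0.40 × 0.05 = 0.02
- Type I error = P(|Z + b/SE| > 1.96), which is about 7.5% for b = 0.01 and about 15.5% for b = 0.02

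**Step 5. Range.** Suppose 90% of positives are accepted as school-based in the control arm and fewer in the screening arm, again with no true difference.

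| Positive contacts, both arms | Accepted, screening arm | Spurious difference (points) | Share of planned 6 points | Type I error |
|---|---|---|---|---|
| 5% | 80% | 0.5 | 8% | 5.6% |
| 5% | 70% | 1.0 | 17% | 7.5% |
| 5% | 50% | 2.0 | 33% | 15.5% |
| 8% | 80% | 0.8 | 13% | 6.6% |
| 8% | 70% | 1.6 | 27% | 11.6% |
| 8% | 50% | 3.2 | 53% | 32% |

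A modest lean does little; a large one is material. Under Section E's definition every spurious difference in this table would be zero by this route.

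**The case against.** The strongest reply is that the statistical plan's primary outcome is a ratio of test results and needs no adjudication. D1's own worked example (2 of 10 contacts infected, 20%) also mentions no review. On that reading the grading is descriptive and cannot bias the main comparison. This stands as far as Section E goes. It does not settle the matter, because D1 names school-based transmission as the outcome and lists this review first among the ways to determine it. D1 also says that the unreviewed weekly counts lack knowledge of household or community exposure, so the review is what separates school infection from other infection.

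Three stronger readings are tempting and are not supported.

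- *The reviewers know the arm.* The documents do not say who the five are or what they know. Collection, calls and interviews are given to unspecified team members.
- *The packets show the school and the reason for testing.* The contact interview and the contact tracer's survey are Appendices 2 and 3, which are not in the text available here. The topics listed in D1 do not include either item by name.
- *The analysis cannot remove the bias.* The Section E ratio and the second method are not exposed to it.

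The standardized definitions are a real safeguard, although their wording is not in the available text either. They limit discretion, but weighing competing exposures still takes judgement. It is also fair to say that the standard error in the working was planned for the unadjudicated outcome and that the reclassification shares are assumed; 40% would be severe with five reviewers and set definitions.

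**Conclusion.** The point holds in a conditional form. The plan has study team members make a partly subjective call on every positive contact, does not mask them to school or arm, and does not say whether or how that call enters the primary outcome. That reviewers could infer the arm is probable, not documented.

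If the adjudicated rate is primary, the assumed shifts of 20% and 40% in one arm give a spurious 1 or 2 points against a planned effect of 6, and a type I error of about 7.5% or 15.5%. These figures rest on 5% positivity in both arms and the planned standard error. If the Section E ratio is primary, the bias by this route is zero. The protection is cheap and the sample size does not change, so the plan should be amended, but this does not by itself put the trial's main result in doubt.

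**What to change.** In D1, *Assessment of School-based Transmission*, state that:

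- an existing team member who does not adjudicate removes school, district, arm and reason for testing from each packet, and keeps the exposure details and the symptom-onset or sample dates that reviewers need;
- the five reviewers classify separately, the majority grade is used, and a tie rule is given (five votes over four grades can split 2-2-1);
- named grades count as transmission.

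In D1 and Section E, state which definition of the primary outcome governs. Report the unadjudicated Section E ratio beside the adjudicated rate as a sensitivity analysis, so that a reader can see how much of any difference comes from the review.

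The cost is redaction time for about 14 to 56 packets per arm (0.02 × 702 = 14; 0.08 × 702 = 56). Masking will not be perfect: asymptomatic detection, visible from the dates, or free-text answers may sometimes still reveal the arm.
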